5. TABLE OF EVENTS

Table 4: Table of Events

Period	Protocol Reference Section	Screening Period	Treatment Period ^b								Follow-up Period ^b		
		Screening ^a	Each 28-day Cycle								End of Treatment (± 3 days)	28-Day Post Treatment Safety Follow-Up	Long-Term Follow-Up (± 14 days)
			Cycles 1 - 2 (± 3 days)				Cycles 3 - 12 (± 3 days) ⁱ		Cycles 13 - 24 (± 3 days) ⁱ				
Day		-28 to 0	1	8	15	22	1	15	1				
Study Entry and General Assessments													
Obtain Informed Consent/Assent	13.3	X	-	-	-	-	-	-	-	-	-	-	
Interactive Response Technology	7.3	X	X	-	-	-	X	-	X	X	-	-	
Enrollment	6.1.5	-	X ^o	-	-	-	-	-	-	-	-	-	
Demographics	6.1.2	X	-	-	-	-	-	-	-	-	-	-	
Inclusion/Exclusion Criteria	4.2, 4.3	X	X ^o	-	-	-	-	-	-	-	-	-	
Complete Medical History	6.1.3	X	-	-	-	-	-	-	-	-	-	-	
Prior Disease Therapies and History	6.1.4	X	-	-	-	-	-	-	-	-	-	-	
Prior/Concomitant Medication and Procedures	8.0	After signing ICF/IAF and until 28-day post-treatment Safety Follow-up Visit										-	
Safety Assessments													
Adverse Events	10	After signing ICF/IAF and until 28-day post-treatment Safety Follow-up Visit										-	
Assessment of Second Primary Malignancy	6.4.2.10	After signing ICF/IAF and until end of Long-term Follow-up Visit										-	
Physical Exam (including vital signs)	6.4.2.1	X	X ^e	-	-	-	X	-	X	X	X	-	
Pomalidomide Education and Counseling ^d	6.4.2.9	X	X	-	-	-	X	-	X	X	X	-	
Height	6.4.2.2	X	X	-	-	-	X	-	X	X	X	-	
Body Weight	6.4.2.3	X	X	-	-	-	X	-	X	X	X	-	
BSA calculation	6.4.2.4	X	X	-	-	-	X	-	X	-	-	-	
Lansky/Karnofsky Performance Status	6.4.2.5	X	X	-	-	-	X	-	X	X	X	-	

Table 4: Table of Events (Continued)

Period	Protocol Reference Section	Screening Period	Treatment Period ^b							Follow-up Period ^b		
		Screening ^a	Each 28-day Cycle							End of Treatment (± 3 days)	28-Day Post Treatment Safety Follow-Up	Long-Term Follow-Up (± 14 days)
			Cycles 1 – 2 (± 3 days)				Cycles 3 - 12 (± 3 days) ⁱ		Cycles 13 - 24 (± 3 days) ⁱ			
Day		-28 to 0	1	8	15	22	1	15	1			
Hematology ^e	6.4.2.6	X	X ^c	X	X	X	X	X	X	X	X	-
Serum blood chemistry ^e	6.4.2.6	X	X ^c	X	X	X	X	X	X	X	X	-
Hepatitis B serology (if applicable)	6.4.2.6	X	-	-	-	-	-	-	-	-	-	-
Pulse oximetry (O ₂ saturation)	6.4.2.7	X	As clinically indicated									-
Serum or Urine β-hCG Testing (FCBP/FCCBP) ^f	6.4.2.9	X ^g	X ^g	X ^o	X ^o	X ^o	X	-	X	X	X	-
Neurological assessment	6.4.2.8	X	X	-	-	-	X	-	X	X	X	-
Treatment Administration, Accountability and Compliance												
Pomalidomide Dispensing	7.1	-	X	-	-	-	X	-	X	-	-	-
Pomalidomide Administration	7.2	-	Days 1-21			-	Days 1-21		Days 1-21	-	-	-
Response Assessments (High-grade glioma, Medulloblastoma and Ependymoma)												
Brain MRI with and without gadolinium	6.4.1	X ^h	-	-	-	-	Day 1 of Cycles 3, 5, 7, 10, 13, 16, 19, 22 and after Cycle 24 ⁱ			X ^j	-	X ^k
Spine MRI with gadolinium	6.4.1	X ^h	-	-	-	-	Day 1 of Cycles 3, 5, 7, 10, 13, 16, 19, 22 and after Cycle 24 ^{i, i}			X ^j	-	X ^k
Cerebrospinal fluid cytology	6.4.1		As clinically indicated ^m									
Response Assessments (DIPG)												
Brain MRI with and without gadolinium	6.4.1	X ^h	-	-	-	-	Day 1 of Cycles 4, 7, 10, 13, 16, 19, 22 and after Cycle 24 ⁱ			X ^j	-	X ^k
Spine MRI with gadolinium	6.4.1	X ^h	-	-	-	-	Day 1 of Cycles 4, 7, 10, 13, 16, 19, 22 and after Cycle 24 ^{i, i}			X ^j	-	X ^k
Cerebrospinal fluid cytology	6.4.1		As clinically indicated ^m									

Table 4: Table of Events (Continued)

Period	Protocol Reference Section	Screening Period	Treatment Period ^b							Follow-up Period ^b		
		Screening ^a	Each 28-day Cycle							End of Treatment (± 3 days)	28-Day Post Treatment Safety Follow-Up	Long-Term Follow-Up (± 14 days)
			Cycles 1 – 2 (± 3 days)				Cycles 3 - 12 (± 3 days) ⁱ		Cycles 13 - 24 (± 3 days) ⁱ			
Day		-28 to 0	1	8	15	22	1	15	1			
Pharmacokinetics – Optional												
Optional Pharmacokinetic blood sampling	6.5	-	-	X ^o	X ^o	-	-	-	-	-	-	-
Follow-Up												
PFS, DoR, OS, drug related SAEs, SPMs, new anticancer therapies	6.3	-	-	-	-	-	-	-	-	-	-	X ⁿ

β-hcg = beta human chorionic gonadotropin; BSA = body surface area; DoR = duration of response; FCBP = females of childbearing potential; FCCBP = female children of childbearing potential; IAF = informed assent form; ICF = informed consent form; MRI = magnetic resonance imaging; O₂ = oxygen; OS = overall survival; PFS = progression free survival; SAE = serious adverse event; SPM = second primary malignancy.

^a Clinical evaluations to establish eligibility can be obtained up to 28 days prior to Cycle 1, Day 1 (first dose of study drug) unless noted otherwise. Brain/Spine MRI assessments can be obtained up to 21 days prior to Cycle 1, Day 1. Assessments should be re-evaluated as needed if there is a change in clinical status.

^b Deviations within the provided study visit windows are allowed unless noted otherwise for a particular assessment.

^c Safety laboratory (hematology and serum blood chemistry) and physical examinations do not need to be repeated on Cycle 1, Day 1 if performed within 7 days of starting treatment, unless clinically indicated. FCBP/FCCBP must have pregnancy test performed within 24 hours prior to the initial dosing of pomalidomide.

^d Can also be conducted verbally via phone from the site. Subjects must also be counseled against sharing pomalidomide and donating blood, semen or sperm during therapy until the 28-day post-treatment Safety Follow-up Visit. Pregnancy counseling and potential risks must be conducted on Day 1 of each cycle prior to pomalidomide dispensing or at a minimum of every 28 days during the Treatment Period.

^e Subjects who experience toxicity should have appropriate laboratory testing at least twice weekly (3 to 4 days apart or more frequently) until the toxicity has resolved. It is the responsibility of the Investigator to obtain and review laboratory results for subject safety, and follow up with subjects in a timely manner.

^f Testing with a sensitivity of at least 25 mIU/mL will be performed in FCBP/FCCBP subjects; refer to Section 6.4.2.9 for details. It is the responsibility of the Investigator to obtain and review pregnancy test results for subject safety, and follow up with subjects in a timely manner. The subject may not receive pomalidomide until the Investigator has verified that the result of the pregnancy test performed on Day 1 (within 24 hours prior to treatment) of every cycle is negative.

^g Obtain 10 to 14 days prior to first dose of study drug and again within 24 hours prior to first dose of study drug. **NOTE:** The pregnancy test 10 to 14 days prior to initiation of pomalidomide may be omitted, at the discretion of the investigator, for any FCCBP/FCBP who has high acuity disease requiring immediate treatment with pomalidomide. The pregnancy test within 24 hours prior to the first dose of pomalidomide is required to be performed.

^h Screening/baseline MRI can be obtained up to 21 days prior to Cycle 1 Day 1.

ⁱ Brain/Spine MRIs can be performed within 7 days prior to scheduled timepoint.

^j Response/MRI assessment will be performed at the End of Treatment Visit only if the subject has discontinued for reasons other than PD and has been more than 8 weeks since their most recent scan/response assessment.

^k Subjects that discontinue treatment prior to disease progression will be followed with MRI tumor assessments every 6 months from treatment discontinuation for the first year off treatment, then annually thereafter until PD, start of a new anticancer therapy, consent/assent is withdrawn, is lost to follow-up, or death.

- ¹ If no spinal or leptomeningeal disease is present at screening/baseline, subsequent spine MRIs will be obtained on Day 1 of Cycle 7, 13, 19 (or within 7 days prior to dosing), after completion of Cycle 24 (or within 7 days prior) and as clinically indicated at the discretion of the primary treating physician. If there is spinal or leptomeningeal disease present at screening/baseline, spine MRIs will be obtained at the same time points as the brain MRI.
- ^m As clinically indicated to follow disease at the discretion of the primary treating physician. It is recommended to follow at the same interval as required MRIs if positive at screening/baseline.
- ⁿ SPMs should be reported regardless of causality. After treatment discontinuation, all subjects will be followed every 3 months from the 28-Day post-treatment Safety Follow-Up Visit for up to 5 years after the last subject enrolled.
- ^o Cycle 1 only

6. PROCEDURES

All procedures will be performed as outlined in the Table of Events (Table 4) and further detailed in the respective protocol referenced sections below. In the table, required assessments are indicated with an “X” at the visits for which the assessments are to be performed. All data obtained from these assessments must be supported in the subject’s source documentation. No electronic case report form (eCRF) will be used as a source document. Scheduled assessments should be completed **prior** to study treatment administration unless noted otherwise.

6.1. Screening Period

Screening evaluations will be performed for all subjects to determine study eligibility. All clinical evaluations to establish eligibility must be performed within 28 days prior to Cycle 1, Day 1 (first dose of study drug), unless noted otherwise. MRI assessments must be performed within 21 days prior to Cycle 1, Day 1. Eligibility waivers to the protocol will not be granted during the conduct of this trial, under any circumstances.

Safety laboratory analyses and all assessments will be performed locally. Screening laboratory values may be repeated within the screening window, if necessary. **If any** laboratory value does not meet eligibility criteria prior to the first dose (Cycle 1, Day 1) of study treatment, the subject will be considered a screen failure. Subjects who fail screening may be rescreened at the Investigator’s discretion. For subjects who are rescreened, a new ICF/IAF will need to be signed and screening procedures will need to be repeated (if rescreening occurs > 28 days prior to the original screening date). A new subject identification (ID) will be issued once the rescreening transaction is registered in Interactive Response Technology (IRT).

The following will be performed at screening as specified in the Table of Events (Table 4), and further detailed in the protocol referenced Section 6.4, after informed consent/assent has been obtained:

- Registration of screening via IRT
- Demographics
- Inclusion/exclusion criteria
- Complete medical history
- Prior disease therapies and history
- Prior/concomitant medications and procedures
- Assessment of adverse events
- Assessment of SPM
- Physical examination including vital signs
- Height
- Body weight
- BSA calculation

- Lansky/Karnofsky performance status. Karnofsky will be utilized for subjects age ≥ 16 years and Lansky will be utilized for subjects age < 16 years.
- Hematology
- Serum blood chemistry
- Hepatitis B serology (if required)
- Oxygen saturation
- Serum (or urine) beta human chorionic gonadotropin (β -hCG) pregnancy testing: Performed in FCCBP/FCBP at screening within 10 to 14 days prior to first dose of study drug and again to assess subject eligibility within 24 hours prior to the first dose of study drug (this pregnancy test can be done on Cycle 1 Day 1). **NOTE:** The pregnancy test 10 to 14 days prior to initiation of pomalidomide may be omitted, at the discretion of the investigator, for any FCCBP/FCBP who has high acuity disease requiring immediate treatment with pomalidomide. The pregnancy test within 24 hours prior to the first dose of pomalidomide is required to be performed. Negative result(s) are **required** to start treatment administration (see Section 6.4.2.9).
- Neurological assessment
- Brain MRI with and without gadolinium (for tumor evaluation of response assessment).
- Spine MRI with gadolinium (for tumor evaluation of response assessment)
- Cerebrospinal fluid cytology (if clinically indicated)
- Pomalidomide education and counseling is required for all subjects at screening. Education and counseling about pregnancy precautions and the potential risks of fetal exposure must be conducted by trained personnel at the site prior to each dispensing of pomalidomide. The individual conducting the training must sign the appropriate counseling form prior to administration of study treatment to document that the education and counseling was performed.

6.1.1. Information to be Collected on Screen Failures

- Informed consent/assent date
- Demographics
- Inclusion and exclusion criteria eligibility information
- Reason for screen failure
- Adverse events. Concomitant medications to treat the AE(s) will be recorded on the eCRF and captured in the source document.

6.1.2. Demographics

Demographics including gender, race, ethnicity, and date of birth, where allowed by local regulations, will be documented at screening only.

6.1.3. Complete Medical History

A complete medical history including evaluation for preceding medical disorders and past (up to 5 years) or present cardiovascular, respiratory, gastrointestinal, renal, hepatic, neurological, endocrine, lymphatic, hematological, immunological, dermatological, psychiatric, genitourinary, obstetrical, surgical history (including those related to disease under study) or any other disorders will also be documented at screening.

6.1.4. Prior Disease History and Therapies

The subject's current disease (ie, diagnosis, date of diagnosis, grading/staging, and histology), as well as all prior disease therapies including surgery, radiation, SCT, chemotherapy, systemic or any other therapy for the subject's disease will be recorded on the respective eCRF at screening.

6.1.5. Enrollment

Prior to enrolling a subject, written informed consent/assent must be obtained, all screening evaluations must be completed, and eligibility criteria must be verified by the Investigator. Once these actions have been completed, the Investigator or designated staff will log into IRT and confirm that the subject still fulfills all the inclusion and exclusion criteria. After enrollment, the subject will retain his/her Subject ID number (Section 7.3.1) during participation in the study.

6.2. Treatment Period

The subject will begin treatment upon re-confirmation of eligibility (ie, safety assessments) and subsequent enrollment. The subject must start treatment within 28 days of signing the ICF/IAF. For all subsequent visits, an administrative window of ± 3 days is permitted unless noted otherwise for a particular assessment. Brain and spine MRI assessments can be conducted within 7 days prior to the scheduled timepoint (ie, during study drug rest period). Study visit windows should take into account the subject's investigational product (IP) supply and administration.

Note: Safety laboratory (hematology, serum blood chemistry) and physical examinations do not need to be repeated on Cycle 1, Day 1 if performed within 7 days of starting treatment unless clinically indicated; however, for FCCBP/FCBP subjects, a urine or serum pregnancy test must be performed to assess subject eligibility 10 to 14 days prior to and again within 24 hours prior to the first administration of pomalidomide. The pregnancy test 10 to 14 days prior to initiation of pomalidomide however may be omitted, at the discretion of the investigator, for any FCCBP/FCBP who has high acuity disease requiring immediate treatment with pomalidomide. The pregnancy test within 24 hours prior to the first dose of pomalidomide is required to be performed (refer to Section 6.4.2.9).

The Treatment Period is defined as the time starting from first study drug administration (Cycle 1, Day 1) until permanent study treatment discontinuation. Subjects will be administered pomalidomide on Days 1 to 21 of each 28-day treatment cycle for a maximum of 24 cycles. Pomalidomide will not be administered on Days 22 through 28 of the 28-day treatment cycle.

The following evaluations will be performed at the frequency specified in the Table of Events (Table 4) and further detailed in the protocol referenced Section 6.4. The evaluations should be performed prior to dosing on the visit day, unless otherwise specified.

- Reconfirm eligibility (Cycle 1, Day 1 only)

- IRT registration (Day 1 of each treatment cycle)
- Enrollment via IRT: Day 1, Cycle 1 only
- Concomitant medications and procedures
- Adverse event evaluation
- Assessment of SPM
- Physical examination (including vital signs)
- Height
- Body weight
- BSA calculation
- Lansky/Karnofsky performance status. Karnofsky will be utilized for subjects age ≥ 16 years and Lansky will be utilized for subjects age < 16 years.
- Hematology
- Serum blood chemistry
- Oxygen saturation (as clinically indicated)
- Serum (or urine) β -hCG pregnancy testing in FCCBP/FCBP (see Section 6.4.2.9)
- Neurological assessment
- Pomalidomide administration
- Brain MRI with and without gadolinium (for tumor evaluation of response assessment)
- Spine MRI with gadolinium (for tumor evaluation of response assessment)
- Cerebrospinal fluid cytology (as clinically indicated)
- Pomalidomide education and counseling. For applicable subjects, confirmation of use of two effective methods of birth control, agree to use condom (male) or confirmation of complete abstinence
- Optional PK blood sampling (Cycle 1, Day 8 and 15 only)

6.2.1. End of Treatment

All subjects discontinuing treatment, regardless of reason, should undergo treatment discontinuation procedures and evaluation as soon as possible after the decision to permanently discontinue treatment has been made.

The following evaluations will be performed as specified in the Table of Events (Table 4) and further detailed in protocol referenced Section 6.4:

- Registration of treatment discontinuation via IRT
- Concomitant medications and procedures

- Adverse event evaluation
- Assessment of SPM
- Physical examination (including vital signs)
- Pomalidomide education and counseling
- Height
- Body weight
- Lansky/Karnofsky performance status. Karnofsky will be utilized for subjects age ≥ 16 years and Lansky will be utilized for subjects age < 16 years.
- Hematology
- Serum blood chemistry
- Oxygen saturation (as clinically indicated)
- Serum (or urine) β -hCG pregnancy testing for FCCBP/FCBP (see Section 6.4.2.9)
- Neurological assessment
- Brain MRI with and without gadolinium (for tumor evaluation of response assessment) will be performed only if subject has discontinued for reasons other than progression of disease and it has been more than 8 weeks since their most recent scan/response assessment
- Spine MRI with gadolinium (if applicable, for tumor evaluation of response assessment) will be performed only if subject has discontinued for reasons other than progression of disease and has been more than 8 weeks since their most recent scan/response assessment
- Cerebrospinal fluid cytology (as clinically indicated)

6.3. Follow-up Period

6.3.1. Safety Follow-up

All subjects will be followed for 28 days after the last dose of treatment for AE reporting, as well as concomitant medications/procedures used to treat the AEs. SAEs made known to the Investigator at any time thereafter that are suspected of being related to study drug will be reported, as described in Section 10.1. At this visit, the following evaluations will be performed as specified in the Table of Events (Table 4) and further detailed in the protocol referenced Section 6.4:

- Concomitant medications and procedures
- Adverse event evaluation
- Assessment of SPM
- Physical examination (including vital signs)

- Pomalidomide education and counseling
- Height
- Body weight
- Lansky/Karnofsky performance status. Karnofsky will be utilized for subjects age ≥ 16 years and Lansky will be utilized for subjects age < 16 years.
- Hematology
- Serum blood chemistry
- O₂ saturation (as clinically indicated)
- Serum (or urine) β -hCG pregnancy testing for FCCBP/FCBP (see Section 6.4.2.9)
- Neurologic examination

6.3.2. Second Primary Malignancy Follow-up Period

Second primary malignancies will be monitored as events of interest and must be reported as SAEs. This includes any SPM, regardless of causal relationship to study drug, occurring throughout the subject's entire participation in the study. Subjects that do not receive treatment (eg, screen failures) will not be followed for SPM. Further details are described in Section 6.4.2.10.

6.3.3. Long-term Follow-up

After permanent study drug discontinuation, all subjects will be followed every 3 months (± 14 days) from the 28-day post-treatment Safety Follow-up Visit for SPMs (regardless of causal relationship), any drug-related SAEs, OS, and start of any new anticancer therapies. Follow-up will continue every 3 months for up to 5 years after the last subject enrollment, unless consent/assent is withdrawn, the subject is lost to follow-up, or death.

Note: The Long-term Follow-up Period may not be terminated because of starting a new anticancer treatment.

In addition, subjects that discontinue treatment prior to disease progression will be followed for MRI tumor response assessments every 6 months from treatment discontinuation for the first year off treatment, then annually thereafter until PD, withdrawal of consent/assent, start of new anticancer therapy, lost to follow up or death, whichever occurs first. These MRI scans will continue to be sent for independent central review.

Survival/long-term follow-up may be conducted by clinic visits, by record review (including public records) and/or telephone contact with the subject, family, or the subject's treating physician.

6.4. Assessment Types

6.4.1. Efficacy Assessments

Brain tumor assessments will be conducted by MRI with and without contrast (ie, gadolinium) using 3 standard MRI sequences (T1-weighted pre- and postcontrast, T2-weighted, FLAIR). A

spine MRI with contrast (ie, gadolinium) will also be performed as specified in Table 4. The neuroradiologist may select the appropriate sequence that best highlights the tumor (T1-weighted postcontrast or T2-weighted or FLAIR) and the same sequence should be used for serial measurements (Section 6.4.1.2). Further details regarding MRI acquisition requirements are outlined in the Imaging Manual.

Brain MRI assessments will be conducted during screening (within 21 days prior to first dose of study treatment) and then on Day 1 of Cycles 3, 5, 7, 10, 13, 16, 19, 22 (or within 7 days prior to dosing), after completion of Cycle 24 (or within 7 days prior) and as clinically indicated. **Note:** For DIPG subjects only, post-baseline brain MRI assessments will be performed on Day 1 of Cycles 4, 7, 10, 13, 16, 19, 22 (or within 7 days prior to dosing), after completion of Cycle 24 (or within 7 days prior) and as clinically indicated.

Spine MRI will be also performed during screening (within 21 days prior to first dose of study treatment) for all subjects. If no spinal or leptomeningeal disease is present at screening, subsequent spine MRIs will be obtained on Day 1 of Cycles 7, 13, 19 (or within 7 days prior to dosing), after completion of Cycle 24 (or within 7 days prior) and as clinically indicated. If there is spinal or leptomeningeal disease present at screening/baseline, spine MRIs will be obtained at the same brain MRI time points specified above.

In addition, if clinically indicated and at the discretion of the Investigator, CSF cytology will also be assessed to follow disease. It is recommended to follow at the same interval as required brain MRIs if positive at initiation of treatment. Corticosteroid use and clinical assessments (ie, neurologic status) will also be considered when determining overall response (Section 6.4.1.7).

A response assessment should be performed at EOT visit if the subject has discontinued for reasons other than progression of disease and it has been more than 8 weeks since their most recent scan/response assessment. Subjects that discontinue treatment prior to disease progression will be followed for MRI tumor response every 6 months from treatment discontinuation for the first year off treatment, then annually thereafter until PD, start new anticancer therapy, withdrawal of consent/assent, lost to follow-up or death, whichever occurs sooner.

The same method of assessment and sequence/technique must be used to characterize each reported target and non-target lesions at baseline and subsequent scans after start of study treatment.

Tumor response will be assessed both locally and by an independent central reviewer (Section 6.4.1.7) according to the criteria described below. The local Investigator's radiological assessment will be used for subject eligibility and treatment decisions. Efficacy based endpoints incorporating tumor assessments (primary and secondary) will be based on the independent central assessment.

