6.4.1.7. Overall Response Assessment

The overall response assessment takes into account response in both target and non-target lesions, the appearance of new lesions, current corticosteroid use (compared to screening/baseline) and neurologic symptoms/examination (clinical status) according to the criteria described in [Appendix C](#).

Subjects who do not meet the criteria for an objective response or disease progression by the end of Cycle 6 (end of Cycle 3 for DIPG subjects) will be considered as having long-term SD.

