Appendix B: Tumor Response Categories for Target and Non-target Lesions

Target Lesions

For the purpose of this study, response criteria for target lesions are defined as follows:

- **Complete Response (CR):**
 - Complete disappearance on MRI of all measurable lesions.
- **Partial Response (PR):**
 - A reduction of $\geq 50\%$ in tumor size by bi-dimensional measurement (taking as reference the baseline measurements) quantified by the sum of the products of the perpendicular diameters of measurable lesions.
- **Stable Disease (SD):**
 - A decrease of $< 50\%$ or an increase of $< 25\%$ in the sum of the products of the perpendicular diameters of measurable lesions and no evidence of new lesions. Response does not meet the criteria for CR, PR or PD.
- **Progressive Disease (PD):**
 - $\geq 25\%$ increase in the bi-dimensional measurement as quantified by the sum of the products of the largest diameters of the measurable lesions taking as a reference the smallest disease measurement recorded since the start of protocol therapy (nadir).

Non-target Lesions

For the purpose of this study, response criteria for non-target lesions are defined as follows:

- **Complete Response (CR):**
 - Disappearance of all non-target lesions.
 - If spine MRI and/or lumbar CSF cytology were previously positive, it must be negative at time of assessment.
- **Incomplete Response/Stable Disease (IR/SD):**
 - The persistence of non-target lesions, stable (no progression) or decrease in size.
 - If spine MRI and/or lumbar CSF cytology were previously positive at baseline and remains positive with no other evidence of PD.
- **Progressive Disease (PD):**
 - The appearance of one or more new lesions and/or unequivocal progression of existing non-target lesions.
 - If spine MRI and/or lumbar CSF cytology were previously negative and became positive.

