6.1. Analysis of Primary Efficacy Endpoint

6.1.1. Objective Response and Long-term Stable Disease Rate

The ORSDR is defined as the percentage of subjects that achieve either a CR, PR or SD maintained for ≥ 6 cycles (≥ 3 cycles for the DIPG tumor type/disease indication) as their best response, divided by the total number of subjects available for the analysis within the given population, eg, subjects contained within the Response Population (primary analysis), the ITT Population, and the Safety Population as outlined within Section 5 of this SAP. The ITT Population will not be used should all enrolled subjects have received at least one dose of study drug. Non-responder subjects are considered subjects with a PD as best response, subjects not having a postbaseline assessment or subjects having not evaluable recorded on their postbaseline assessment(s). The corresponding 2-sided, 95% Clopper-Pearson confidence interval (CI) will also be provided.

Calculation of SD duration starts at the time of first dose of pomalidomide and continues until the date of the first observation of PD is recorded or death due to any cause, regardless of whether the subject achieves a CR and/or PR within that period, or until the date of the last disease assessment if no PD or death is recorded; if the difference is ≥ 6 cycles (≥ 3 cycles for the DIPG tumor type/disease indication), ie, the subject has not had a documented PD before Cycle 7, Day 1 (Cycle 4, Day 1 for the DIPG tumor type/disease indication) and has completed 6 cycles of pomalidomide (3 cycles for the DIPG tumor type/disease indication), then the SD will be considered as being maintained for ≥ 6 cycles (≥ 3 cycles for the DIPG tumor type/disease indication).

For identification of PD for this SD duration calculation, PD is classified as a PD as observed during a response assessment (both during the Treatment Period and the Follow-up Period if applicable); the first time this occurrence is observed is selected as the PD date.

Disease assessments recorded on or after start of a new anticancer therapy will not be considered, nor will disease assessments reported after a PD has been observed.

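### In DIPG subjects with a clear baseline spine, no spine MRI is scheduled before the primary endpoint is read at Cycle 4, so clinically silent spine-only progression can be scored as a success

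*Protocol*

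**What the plan says.** **Brain schedule.** Protocol 6.4.1 (and 3.1) gives DIPG its own brain imaging times: "For DIPG subjects only, post-baseline brain MRI assessments will be performed on Day 1 of Cycles 4, 7, 10, 13, 16, 19, 22".

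**Spine schedule.** All subjects have a spine MRI at screening. After that, the same section says: "If no spinal or leptomeningeal disease is present at screening, subsequent spine MRIs will be obtained on Day 1 of Cycles 7, 13, 19". The sentence continues and the next one opens: "after completion of Cycle 24 (or within 7 days prior) and as clinically indicated. If there is spinal or leptomeningeal disease present at screening/baseline"; in that case the spine follows the brain schedule. The Table 4 footnote repeats the rule for a clear spine, again without a DIPG exception: "If no spinal or leptomeningeal disease is present at screening/baseline, subsequent spine MRIs will be obtained on Day 1 of Cycle 7, 13, 19". SAP Table 3 carries the same footnote. CSF testing is not routine: "if clinically indicated and at the discretion of the Investigator, CSF cytology will also be assessed to follow disease".

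**Endpoint.** Protocol 6.4.1.7 takes subjects with neither an objective response nor "disease progression by the end of Cycle 6 (end of Cycle 3 for DIPG subjects) will be considered as having long-term SD". SAP 6.1.1 requires that "the subject has not had a documented PD before Cycle 7, Day 1 (Cycle 4, Day 1 for the DIPG tumor type/disease indication"), and that the matching number of cycles has been completed. It dates PD to the first assessment at which it is observed.

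**Spinal disease is part of response.** Protocol 3.1 has radiographic response cover brain and spine. Appendix B lists under non-target PD: "If spine MRI and/or lumbar CSF cytology were previously negative and became positive". Table 10 in Appendix C allows CR, PR or SD only when there is no new lesion.

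**The concern.** The DIPG brain scans fit the three-cycle endpoint. The routine spine scans for subjects with a clear baseline spine do not. For these children no scheduled test looks at the spine between screening and the endpoint read, although the protocol's own criteria make new spinal disease PD. A child with a stable or shrinking pontine lesion and new, symptomless spinal spread would be scored a success.

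Such an error runs one way only: a missed progression can add a success and cannot remove one. It matters because the DIPG decisions rest on small counts, at least 2 of 9 to enter Stage 2 and at least 5 of 20 to call the drug effective, so one child can change either decision.

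**Working it through.** **1. Dates.** Cycles are 28 days (Protocol 1.3.3), so planned Day 1 of cycle k is study day 1 + 28(k − 1).
- DIPG endpoint read, Cycle 4 Day 1: 1 + 28 × 3 = Day 85.
- First routine spine MRI with a clear baseline spine, Cycle 7 Day 1: 1 + 28 × 6 = Day 169.
- Gap: 169 − 85 = 84 days = 12 weeks (about 11 if only the spine scan uses its 7-day early window).

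**2. Does a later finding correct the score?** No. Under SAP 6.1.1, SD duration runs from first dose to the first observed PD. Spinal PD first seen at Cycle 7 gives a duration of about six cycles, against the three that DIPG needs. A CR or PR recorded at Cycle 4 also stands as best response.

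**3. The plan's own design, reproduced.** Inputs from Protocol 9.3: lower boundary 10%, upper boundary 40%, 9 + 11 subjects, continue at 2 or more of 9, positive at 5 or more of 20.

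P(positive) = Σ over x = 2 to 9 of P(X₁ = x; n = 9) × P(X₂ ≥ 5 − x; n = 11), where the second factor is 1 once x ≥ 5.

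At p = 0.10:
- x = 2: 0.1722 × 0.0896 = 0.0154
- x = 3: 0.0446 × 0.3026 = 0.0135
- x = 4: 0.0074 × 0.6862 = 0.0051
- x ≥ 5: 0.0009
- Sum: 0.0349

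The same formula at p = 0.40 gives 0.902. An exhaustive search for Simon's optimal design under 5% and 90% returns the stated one, so the plan's figures hold. The chance of entering Stage 2 at 10% is 1 − (0.9⁹ + 9 × 0.1 × 0.9⁸) = 0.225.

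**4. Illustration of size.** Let m be the share of evaluable DIPG subjects who would otherwise be successes but have unseen spinal PD at Cycle 4. The documents do not give m, so it is an assumption. The observed rate is 10% + m.

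| Assumed m (points) | Observed rate | P(enter Stage 2) | P(declared positive) |
|---|---|---|---|
| 0 | 10% | 22.5% | 3.5% |
| 1 | 11% | 26.0% | 5.0% |
| 2 | 12% | 29.5% | 6.75% |
| 3 | 13% | 33.0% | 8.9% |
| 5 | 15% | 40.1% | 14.1% |
| 10 | 20% | 56.4% | 31.5% |

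The unrounded value at m = 1 is 4.96%, so a missed share just over 1 point takes the false-positive chance past the nominal 5%. Five points is 0.05 × 20 = one child in a full stratum.

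**The case against.** A reader might infer that any new spinal or leptomeningeal progression in DIPG goes unseen and is scored as long-term SD. The documents do not support that. Spine MRI may be done whenever clinically indicated. Table 4 puts a neurologic assessment on Day 1 of every cycle, and Table 10 makes neurologic decline PD on its own. Protocol 8.1.2 asks for imaging within 72 hours when a subject on steroids needs more for worsening neurologic symptoms. The contrast-enhanced brain MRI at Cycle 4 looks for new intracranial lesions, including leptomeningeal ones. DIPG subjects with spinal disease at baseline are already scanned at Cycle 4. What escapes is spread that is both clinically silent and confined to the spine.

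These safeguards have limits. The 72-hour rule can be met by a brain scan alone. For SD duration, SAP 6.1.1 counts only PD observed at a response assessment, whereas SAP 6.2.3 and 6.2.4 also accept PD from the disposition pages.

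A reader might also infer that the other three strata are fully protected, or that the spine schedule was carried over to DIPG by oversight. The first is only partly true. In those strata a CR or PR at Cycle 3 or 5 also counts without a routine spine scan if the baseline spine was clear. Read literally, the SAP also asks for no PD before Cycle 7 Day 1, so spinal PD first seen on that day, after earlier SD, need not reverse the score. On the second, the documents give no reason for the schedule.

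The objection to the size also stands. Missed shares of 2 and 5 points would mean that 2/12 = 17% and 5/15 = 33% of apparent DIPG successes hid silent spinal progression, and nothing in the documents supports such figures. Zero belongs in the range. The false-positive reading also takes the 10% boundary to refer to an endpoint that includes the spine; Protocol 9.3 gives no source for it.

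**Conclusion.** The point holds in a limited form. For DIPG subjects with a clear spine at screening, the first scheduled post-baseline spine MRI comes 12 weeks after the primary endpoint is read. Clinically silent, spine-only progression can therefore be counted as long-term SD or objective response, and later detection does not undo it. The schedule gap and the direction of the bias are certain; the frequency is unknown. The range of 3.5% (nothing missed) to 14.1% (5 points missed) for a false declaration at a true 10% rate is an illustration resting wholly on the assumed share, not an estimate of the trial's error rate. The gap affects one stratum and is cheap to close, so it merits a change without calling the design into question.

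**What to change.** For DIPG subjects with no spinal or leptomeningeal disease at screening, add the first post-baseline spine MRI to the existing Cycle 4 Day 1 brain session. Place later spine scans at existing brain sessions, for example Cycles 10, 16 and 22 and after Cycle 24, which keeps six cycles (24 weeks) between the Cycle 4, 10, 16 and 22 scans. Change Protocol 3.1, 6.4.1 and Table 4 footnote l, and SAP Table 3. Spinal PD found at that first assessment makes PD the best response, and SAP 6.1.1 already counts such a subject as a non-responder.

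**Cost.** The Cycle 4 session is longer, possibly under sedation (Protocol 8.2.4 foresees propofol for MRI). Children who leave between Cycles 4 and 7 have a spine scan they would not otherwise have had. Over 24 cycles there is at most one more spine scan (Cycles 4, 10, 16, 22 and after 24, against 7, 13, 19 and after 24). There is no longer a routine spine scan at Cycle 7, so silent spread arising after Cycle 4 may wait until Cycle 10, which can affect PFS and duration of response.

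**If the schedule cannot change.** Add to SAP 6.1.1 a sensitivity analysis of the DIPG ORSDR that counts spinal PD found up to and including the Cycle 7 scan as failure. It costs only SAP text. It misses children who leave before Cycle 7 and also counts against the drug any spread that arose after Cycle 4, so report how many Cycle 4 successes had no later spine scan.
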